Appendix C Detailed statistical methodology for pattern mixture model

For the Q2W dosing regimen cohort, as a sensitivity analysis of the primary efficacy endpoint (ie, percent change from baseline to Week 24 in LDL-C), a pattern-mixture model approach will be used, with a different imputation strategy applied for missing LDL-C values during the on-treatment period (ie, within the time period from the first IMP injection up to the day of the last double-blind injection +21 days) and missing LDL-C values after treatment discontinuation (ie, after the day of last double-blind injection +21 days as described above) based on the following assumptions:

- Patients within 21 days (see above) of their last double-blind IMP injection would continue to show benefit from treatment similar to that observed at the scheduled time point. Therefore, LDL-C values missing during the on-treatment period will be considered "Missing at Random" and imputed using a model estimated using all samples collected on treatment.
- Patients who stopped taking their study treatment no longer benefited from it in the future, and thus tended to have LDL-C values returning to baseline. Thus LDL-C values missing after treatment discontinuation will be imputed based on patient's own baseline value.

For patients who permanently discontinued the treatment due to the COVID-19 pandemic, missing post-treatment data will be considered "Missing at Random" and imputed based on other on-treatment measurements in the same treatment group.

For the Q4W dosing regimen cohort, the same approach will be taken except that the on-treatment period will be defined as the time period from the first double-blind IMP injection up to the day of the last double-blind injection +35 days for patients with a last double-blind injection before the switch to Q2W regimen (actual of sham), +21 days otherwise. The two assumptions made for the Q2W dosing regimen cohort prevail for the Q4W dosing regimen cohort as well.

The assumptions for this approach are based on the following considerations:

- Missing values during the on-treatment period are mostly consecutive to:
 - Visits performed outside of the pre-specified time-window,
 - No blood sample available although visit was done,
 - LDL-C not measurable due to technical reasons.

In addition, these missing data are often intermittent, ie, followed by LDL-C values collected at subsequent visits. It is therefore considered reasonable to assume that these missing data were "At Random".

• Phase 2 studies DFI11565 and R727-CL-1003 included a prospective assessment of calculated LDL-C during the follow-up period after a 12-week treatment period. These studies showed that after treatment discontinuation, the average calculated LDL-C returned

to baseline level within 4 weeks after ceasing alirocumab treatment (See Figure 3 and Figure 4).

Figure 3 - Study DFI11565: calculated LDL-C mean (+/- SE) percent change from baseline

Figure 4 - Study R-727-CL-1003: calculated LDL-C mean (+/- SE) percent change from baseline

For each dosing regimen cohort, missing LDL-C values will be imputed 100 times to generate 100 complete data sets. The percent change from baseline to Week 24 will be derived from observed and imputed LDL-C at this time point. The completed data sets will be analyzed using a linear

Property of the Sanofi Group - strictly confidential

Statistical Analysis Plan SAR236553/RGN727-EFC14643 - alirocumab 19-Feb-2021 Version number: 2

regression model with the baseline LDL-C value as continuous covariate. Combined mean with their corresponding standard errors (SEs) and 97.5% CIs will be provided through the SAS MIANALYZE procedure using Rubin's formulae (8).

Imputation of missing data during the on-treatment period

Missing LDL-C values during the on-treatment period will be imputed from other on-treatment measurements assuming Missing At Random, using SAS MI procedure.

Only LDL-C values collected during the on-treatment period will be included in the imputation model. This way, missing LDL-C values during the on-treatment period will be imputed based solely on observed on-treatment LDL-C values.

The imputation model will include the baseline LDL-C value and all LDL-C values at pre-specified visits. Since the pattern of missing data is necessarily non-monotone, a Monte-Carlo Markov Chain (MCMC) method is used. A minimum value of 0 will be specified in order to avoid negative imputed LDL-C values.

A sample SAS code is provided below:

proc mi data=DATAIN out=DATAOUT nimpute=100 minimum=0;

var LDL_BASE LDL_W8 LDL_W12 LDL_W24 ;

run;

As stated above, the input dataset DATAIN will include only LDL-C values collected during the on-treatment period. Any LDL-C values collected during the post-treatment period will be excluded from the input dataset. In practice, the MI procedure generates imputed values for all missing values (whether on-treatment or post-treatment), but only imputed values during the-on-treatment period will be kept in the final datasets that will be described using means and their corresponding. Imputed values during the post-treatment period will be discarded and replaced by imputed values described in the next paragraph.

Imputation of missing data after treatment discontinuation

Missing LDL-C values during the post-treatment period will be imputed assuming LDL-C values would on average return to baseline values.

For each patient, missing post-treatment LDL-C values will be imputed 100 times, using a random draw from a normal distribution, with mean equal to patient's own baseline value and variance equal to the conditional variance at the specific time-point, given the baseline value.

Let Y_0 and Y_1 denote the LDL-C at baseline and at the specific time-point respectively. Since Y_0 and Y_1 are assumed to have a bivariate normal distribution, the conditional variance of Y_1 given Y_0 is:

$$Var(Y_1|Y_0 = y_0) = \sigma_1^2(1 - \rho^2)$$

Where σ_1^2 denotes the variance of Y1 and ρ the coefficient of correlation between Y₀ and Y₁.

The conditional variance will be estimated from observed data at the specific time-point.

During the random generation process, a minimum value of 0 will also be applied in order to avoid negative imputed LDL-C values.

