For the Q2W dosing regimen cohort, multiple imputations will be used with different imputation strategies applied to LDL-C values missing during the on-treatment period (ie, within the time period from the first double-blind IMP injection up to the day of last double-blind injection +21 days) versus LDL-C values missing after treatment discontinuation (ie, after the day of last double-blind injection +21 days) based on the following assumptions:

- Patients within 21 days of their last double-blind IMP injection would continue to show benefit from treatment similar to that observed at the scheduled time point. Therefore, LDL-C values missing during the on-treatment period (eg, samples obtained out-side the specified window, no blood sample available although visit was performed, etc.) should be considered "Missing At Random" and imputed based on other on-treatment measurements.
- Patients who stopped taking their study treatment no longer benefited from it after discontinuation, and thus tended to have LDL-C values returning to baseline. Therefore, LDL-C values missing more than 21 days after treatment discontinuation should be imputed based on patient's own baseline value.

For patients who permanently discontinued the treatment due to the COVID-19 pandemic, missing post-treatment data will be considered "Missing at Random" and imputed based on other on-treatment measurements in the same treatment group.

Missing LDL-C values will be imputed 100 times to generate 100 complete data sets. The percent change from baseline to Week 24 will be derived from observed and imputed LDL-C at this time point. The completed data sets will be analyzed using an ANCOVA model, with unequal variances by treatment group (except if convergence issue), with treatment group (alirocumab, placebo) and randomization strata (previous participation [yes or no] to DFI14223 study, baseline body weight [<50 or \geq 50 kg]) as fixed effects, and the baseline LDL-C value as continuous covariate. The results from the 100 analyses will be combined using Rubin's formulae (8).

For the Q4W dosing regimen cohort, the same approach will be taken with the following differences:

- The on-treatment period will be defined as the time period from the first IMP injection up to the day of the last double-blind injection +35 days for patients with a last double-blind injection before the switch to Q2W regimen (actual of sham), +21 days otherwise.

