- The ANCOVA model will include treatment group (alirocumab, placebo) and randomization strata (baseline body weight [<50 or ≥50 kg]) as fixed effects, and the baseline LDL-C value as continuous covariate.

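### SAP Appendix C imputes missing on-treatment LDL-C without treatment group, and its analysis and COVID-19 steps conflict with the rules stated for the same pattern-mixture analysis

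*SAP*

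**What the plan says.** SAP Section 2.4.4.1.4 defines the pattern-mixture sensitivity analysis and refers to Appendix C for detail. Values missing on treatment are treated as missing at random. Values missing after discontinuation are drawn around the patient's own baseline.

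- **On-treatment imputation.** Appendix C assumes that these patients "would continue to show benefit from treatment similar to that observed at the scheduled time point". It fits one model to all on-treatment samples: "The imputation model will include the baseline LDL-C value and all LDL-C values at pre-specified visits". The sample PROC MI code has "var LDL_BASE LDL_W8 LDL_W12 LDL_W24", with no treatment variable and no BY statement.
- **Analysis of the completed data.** Section 2.4.4.1.4 says, for Q2W, "The completed data sets will be analyzed using an ANCOVA model, with unequal variances by treatment group", with treatment, strata and baseline in the model. For Q4W, "The ANCOVA model will include treatment group (alirocumab, placebo) and randomization strata", again with baseline. Appendix C instead names a linear "regression model with the baseline LDL-C value as continuous covariate" and reports a combined mean with a 97.5% CI.
- **COVID-19 discontinuations.** Section 2.4.4.1.4 and the opening of Appendix C both have missing post-treatment values "imputed based on other on-treatment measurements in the same treatment group". The operating step later in Appendix C reads "Imputed values during the post-treatment period will be discarded and replaced by imputed values described in the next paragraph". The replacement is a baseline-centred draw for each patient, with no exception.

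**The concern.** An imputation model that omits treatment, when the analysis then estimates a treatment difference, draws each missing value from a mixture of the two arms. Earlier visits carry the treatment information only in part, so imputed alirocumab values come out too high and imputed placebo values too low. That does not fit the stated premise of continued benefit. The omission cannot be read as shorthand: Section 2.4.4.1.4 attaches the same-group condition only to COVID-19 discontinuations, while the SAP's other imputation model, in Section 2.4.4.2.2, lists treatment group explicitly.

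Section 2.4.4.1.1 names this analysis as the check on non-ignorable missingness, and Section 2.4.4.2.1 extends it to the normally distributed key secondary endpoints. If its result differs from the MMRM, the reader should be able to attribute the gap to the return-to-baseline assumption. As written, part of the gap would come from the on-treatment step. Section 1.6 attributes the unequal-variance ANCOVA and the COVID-19 rule to regulatory feedback, and Appendix C's operating steps deliver neither.

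**Working it through.** **Inputs from the documents** (Protocol 11.1, SAP 1.3): difference 30 points, SD 25, two-sided alpha 0.025, 2:1 allocation, power stated as 92% with 30 vs 15, planned size 50 vs 25 per cohort.

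**Assumptions, not in the documents:** between-visit correlation r of 0.3 to 0.7; 5 to 20% of Week 24 values missing on treatment, equally in both arms; the same effect at every visit; baseline LDL-C 180 mg/dL with SD 40.

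**The plan's own figure.** SE = 25 × √(1/30 + 1/15) = 7.91 and 30/7.91 = 3.79. Against the critical value 2.24, the normal approximation gives 94.0% power and the noncentral t with 43 df gives 92.5%. The stated 92% is reproduced.

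**Pull in the imputed values.** Work on the percent-change scale, with baseline balanced between arms. Without treatment in the model, the between-arm spread enters the pooled moments:

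- pooled variance V = 625 + (2/3)(1/3)(30²) = 825
- pooled covariance C = 625r + 200
- difference among imputed patients, Week 8 observed only: 30 × C/V
- the same with Weeks 8 and 12 observed: 30 × 2C/(V + C)
- no post-baseline value observed: 0

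| r | C | Week 8 only | Weeks 8 and 12 |
|---|---|---|---|
| 0.3 | 387.5 | 14.1 | 19.2 |
| 0.5 | 512.5 | 18.6 | 23.0 |
| 0.7 | 637.5 | 23.2 | 26.2 |

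The true value is 30. The pull is uneven. At r = 0.5 with Weeks 8 and 12 observed, the slope is 1025/1337.5 = 0.766 and the pooled mean is -20. The imputed means are -20 - 0.766 × 10 = -27.7 on alirocumab (true -30) and -20 + 0.766 × 20 = -4.7 on placebo (true 0). Placebo moves more because of the 2:1 allocation. A large-sample simulation on the LDL-C scale (400,000 vs 200,000) gave the same differences to within 0.1, and adding treatment restored -30.0 to -30.1.

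**Shift in the cohort estimate** = missing fraction × shortfall. At 10% missing:

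- Weeks 8 and 12 observed: 0.1 × (30 - 26.2) to 0.1 × (30 - 19.2) = 0.4 to 1.1 points
- Week 8 only: 0.1 × (30 - 23.2) to 0.1 × (30 - 14.1) = 0.7 to 1.6 points
- nothing post-baseline: 0.1 × 30 = 3.0 points

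**Trial size.** 1,500 simulated trials per scenario, 50 vs 25, 20 imputations with minimum 0, ANCOVA on treatment and baseline, Rubin's rules. Shift without versus with treatment in the imputation model, in points:

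| r | Observed | 5% missing | 10% | 20% |
|---|---|---|---|---|
| 0.3 | Weeks 8 and 12 | 0.58 | 1.17 | 2.44 |
| 0.3 | Week 8 | 0.90 | 1.76 | 3.52 |
| 0.7 | Weeks 8 and 12 | 0.23 | 0.40 | 0.89 |
| 0.7 | Week 8 | 0.41 | 0.72 | 1.51 |

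The standard error is 6.3 to 7.3, so the range is 0.04 to 0.48 SE. With treatment included, the mean estimate is -29.8 to -30.3. A second simulation (250 trials, 10 imputations, baseline SD 45, r of 0.5 and 0.7) agrees: at 8% missing the loss is 0.3 to 0.6 points if only Week 24 is missing, 0.5 to 0.8 if Weeks 12 and 24 are, and about 2.4 if all post-baseline values are.

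**COVID-19 step.** With a mean change of -30 on alirocumab, a baseline-centred value in place of a same-arm value moves the arm mean by 30/50 = 0.6 points per patient.

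**The case against.** The core omission is hard to dispute; the case on the other side concerns weight.

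- **The two conflicts can be read away.** Section 2.4.4.1.4 specifies the ANCOVA fully, Section 1.6 confirms it as a deliberate version 2 change, and a baseline-only regression gives no treatment comparison, so a statistician would not take it as the test. A specific COVID-19 rule would normally override a general replacement step. This is fair as to intent. But a programmer following Appendix C would implement something else, and its imputation model cannot supply same-arm draws at all.
- **Most of the benefit survives.** At r = 0.5 with Weeks 8 and 12 observed, imputed alirocumab patients keep 27.7 of 30 points. True, but the between-arm difference is what counts, and it falls to 23.0.
- **The upper figures stack assumptions.** A shift of 3.5 points needs 20% missing on treatment, Week 12 missing in all those patients, and r = 0.3. Appendix C calls such gaps often intermittent, the Week 24 window covers days 155 to 182, and unscheduled values count. This stands. With Weeks 8 and 12 observed and 5 to 10% missing, the shift is 0.2 to 1.2 points.
- **The key secondary endpoints are not quantified.** This also stands. Apo B, for example, has no Week 8 sample, so the LDL-C figures do not transfer directly.

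**Conclusion.** The concern holds as stated. The on-treatment imputation in Appendix C is wrong as written, and its analysis model and COVID-19 step conflict with Section 2.4.4.1.4, the COVID-19 step also with Appendix C's own opening. The simulated bias towards zero is 0.4 to 1.8 points at 10% missing when an earlier visit is observed, and 0.2 to 3.5 points over 5 to 20% missing. These sizes rest on assumed correlations and missing rates. The textual conflicts and the direction of the bias, given a real treatment effect, do not.

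The bias is conservative for superiority. The primary MMRM, the alpha split and the testing hierarchy are unaffected, and the return-to-baseline part still works because post-treatment values are replaced separately. What is lost is a clean reading of the SAP's one not-missing-at-random analysis. It should be fixed, but it does not threaten the primary conclusion.

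**What to change.** Amend Appendix C in three places:

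1. Within each cohort, run the on-treatment imputation by treatment group, or add treatment group to the imputation model and the sample code, as Section 2.4.4.2.2 already does.
2. Replace the baseline-only regression and combined mean with the Section 2.4.4.1.4 ANCOVA, and report the LS-mean difference with its 97.5% CI.
3. Exempt patients who discontinued because of COVID-19 from the discard-and-replace step, so that they keep draws from the arm-specific model.

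It would also help to say whether the conditional variance for post-treatment draws is estimated within arm. The cost is a few lines of SAP wording and code before the first-step analysis, with no effect on data collection or patients.

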Appendix D List of MedDRA terms for CMQs

Table 8 - Selected PTs from SMQ "Optic nerve disorders" including in the CMQ for neurologicevents

MedDRA Term Label	Preferred Term Code		
Benign neoplasm of optic nerve	10057424		
Optic atrophy	10030910		
Optic discs blurred	10030923		
Optic nerve disorder	10061322		
Optic nerve injury	10030938		
Optic nerve neoplasm	10053645		
Optic nerve operation	10053272		
Optic neuropathy	10061323		
Papillitis	10033708		
Pseudopapilloedema	10037141		
Subacute myelo-opticoneuropathy	10058009		
Toxic optic neuropathy	10044245		
Visual evoked potentials abnormal	10047549		
Amaurosis fugax	10001903		
Blindness	10005169		
Blindness unilateral	10005186		
Colour blindness acquired	10010051		
Colour vision tests abnormal	10010056		
Cranial nerve injury	10061094		
Delayed myelination	10076456		
Fundoscopy abnormal	10017520		
Hemianopia	10019452		
Hemianopia heteronymous	10019455		
Hemianopia homonymous	10019456		
Loss of visual contrast sensitivity	10064133		
Neuro-ophthalmological test abnormal	10029256		
Night blindness	10029404		
Ophthalmological examination abnormal	10056836		
Optic pathway injury	10030949		
Optical coherence tomography abnormal	10073561		

Property of the Sanofi Group - strictly confidential

MedDRA Term Label	Preferred Term Code
Quadrantanopia	10077820
Visual acuity reduced	10047531
Visual acuity reduced transiently	10047532
Visual acuity tests abnormal	10047534
Visual field defect	10047555
Visual field tests abnormal	10047567
Visual impairment	10047571
Visual pathway disorder	10061411

 Table 9 - CMQ "Neurocognitive disorders – FDA's recommendation"

MedDRA level	MedDRA Code	MedDRA Term Label
PTCD	10001949	Amnesia
PTCD	10061423	Amnestic disorder
PTCD	10002711	Anterograde Amnesia
PTCD	10078497	Neuropsychiatric symptoms
PTCD	10008398	Change in sustained attention
LLTCD	10009843	Cognitive Deterioration
PTCD	10057668	Cognitive Disorder
LLTCD	10010300	Confusion
LLTCD	10048321	Confusion Aggravated
PTCD	10010305	Confusional State
PTCD	10012218	Delirium
PTCD	10012267	Dementia
PTCD	10012271	Dementia Alzheimer's type
LLTCD	10012290	Dementia Nos
LLTCD	10012291	Dementia Nos Aggravated
LLTCD	10012292	Dementia of the Alzheimer's type NOS
PTCD	10067889	Dementia with Lewy Bodies
PTCD	10013395	Disorientation
PTCD	10013496	Disturbance in attention
PTCD	10070246	Executive dysfunction
PTCD	10068968	Frontotemporal Dementia
LLTCD	10058669	Global Amnesia
PTCD	10021402	Illogical Thinking

Property of the Sanofi Group - strictly confidential

MedDRA level	MedDRA Code	MedDRA Term Label
PTCD	10071176	Impaired reasoning
PTCD	10021630	Incoherent
PTCD	10023236	Judgement impaired
PTCD	10027175	Memory Impairment
PTCD	10027374	Mental Impairment
LLTCD	10027376	Mental Impairment Nos
LLTCD	10048345	Mental State Abnormal Aggravated
PTCD	10048294	Mental Status Changes
PTCD	10065424	Mini Mental Status Examination Abnormal
PTCD	10036631	Presenile Dementia
PTCD	10038965	Retrograde Amnesia
PTCD	10039966	Senile Dementia
LLTCD	10039967	Senile Dementia Nos
LLTCD	10040602	Short-term Memory Loss
PTCD	10043431	Thinking Abnormal
LLTCD	10043438	Thinking Slowed
PTCD	10044380	Transient Global Amnesia
PTCD	10057678	Vascular Dementia

Appendix E Z-score calculation formula for Cogstate Battery test

Z-Score: Comparison of Individual Scores to Normative Data

- Performance on each Cogstate test can be standardized relative to age matched normative data (i.e., the score will be converted to a z-score by subtracting the age matched mean from Cogstate's normative sample and dividing by the age matched standard deviation (SD) from the same normative sample)
- The multiplicand equals 1 for tests for which a higher score is indicative of better cognitive performance (i.e., OCL) and -1 for tests where a lower score is indicative of better cognitive performance (i.e., DET, IDN, GML).
- The z-score will be calculated as follows:

$$z - Score(z_{ijt}) = \frac{(x_{ijt} - \bar{x}_{1t})}{\sigma_{1t}} * Multiplicand$$

Where:

t = is the test indicator

i = indexes subject i

j = indexes the jth assessment for subject i

x = cognitive score

 \bar{x}_{it} = mean performance score of the age-matched normative sample for test t

 σ_{it} = Standard Deviation of the age-matched normative sample for test t

Appendix F Cogstate normative data

Table 1. Summary normative data for the Detection test. The primary outcome for this test is Reaction Time (Log10 transformation)

Age (Years)	N	Mean	SD	WSD
8	22	2.63129	0.13746	0.04997
9	32	2.58581	0.13506	0.04997
10	1,085	2.56241	0.08007	0.04997
11	1,548	2.53830	0.07896	0.04997
12	2,134	2.52938	0.07682	0.04997
13	2,785	2.51597	0.07535	0.04997
14	7,876	2.51298	0.08101	0.04997
15	7,708	2.50910	0.07674	0.04997
16	6,541	2.50538	0.07644	0.04997
17	5,986	2.50197	0.07528	0.04997

Table 2. Summary normative data for the Identification test. The primary outcome for this test is Reaction Time (Log10 transformation)

Age (Years)	N	Mean	SD	WSD
8	22	2.84589	0.11548	0.04210
9	32	2.80141	0.09222	0.04210
10	1,085	2.76101	0.07096	0.04210
11	1,548	2.73223	0.07068	0.04210
12	2,134	2.71368	0.06719	0.04210
13	2,785	2.69591	0.06782	0.04210
14	7,876	2.68636	0.06954	0.04210
15	7,708	2.67744	0.06687	0.04210
16	6,541	2.67182	0.06561	0.04210
17	5,986	2.66634	0.06456	0.04210

Table 3. Summary normative data for the One Card Learning test. The primary outcome for this test is Accuracy (Arcsine transformation)

Age (Years)	N	Mean	SD	WSD
8	15	0.91684	0.10775	-
9	16	0.94297	0.16884	-
10	1,085	0.96886	0.08819	0.11788
11	1,548	0.97218	0.08805	0.11788
12	2,134	0.97878	0.08754	0.11788
13	2,785	0.97863	0.08762	0.11788
14	7,876	0.97449	0.08567	0.11788
15	7,708	0.97758	0.08539	0.11788
16	6,541	0.98386	0.08588	0.11788
17	5,986	0.98932	0.08719	0.11788

Table 4. Summary normative data for the Groton Maze Learning Test. The primary outcome for this test is Total Errors

Age (Years)	N	Mean	SD	WSD
8	15	75.60	23.52	-
9	20	73.20	18.28	-
10	31	61.29	21.31	-
11	36	62.97	18.48	-
12	25	55.56	13.71	-
13	20	54.35	13.05	-
14	22	44.32	17.83	-
15	21	47.33	19.15	-
16	45	48.31	20.06	-
17	27	51.11	10.37	-

